10.2.2 Outcomes

10.2.2.1 Safety outcomes

The proportion of subjects experiencing one or more adverse events (AE) prior to treatment, one or more treatment-emergent (TE, defined as occurring any time after first dose of study drug) AEs, one or more severe TE AEs, one or more serious TE AEs (SAE), one or more TE AEs of special interest (AESI, including gout, gouty arthritis, and kidney stones), and one or more AEs classified by MedDRA system organ class, higher level term, and preferred term over 24 weeks in the inosine group will be compared to the placebo group using one-tailed Fisher's exact tests at $\alpha = 0.05$. The proportion of subjects experiencing one or more TE clinically significant abnormal labs for each safety assay performed or clinically significant abnormal vital signs for each vital sign monitored over 24 weeks in the inosine group will be compared to the placebo group using Fisher's exact tests. As a sensitivity analysis, we will also analyze event rates using negative binomial models for each type of event, adjusting for each participant's length of follow-up.

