4 STUDY DESIGN

4.1 Overall Study Design and Plan

During the enrollment period, approximately 60 subjects will be screened at up to three (3) Northeast ALS Consortium (NEALS) Centers in the United States. Approximately 30 of these subjects are expected to be found eligible for study enrollment and will be randomized 2:1 to receive inosine or placebo. Per study protocol, the aim is to elevated serum urate levels only in those subjects whose baseline urate level falls below the predicted median for this population. Approximately 30 subjects will receive inosine or placebo for 20 weeks (administered in the form of 500 mg capsules, 1 to 6 capsules a day for a total daily dose of up to 3 gm). The dose of inosine will be titrated to target urate levels of 7-8 mg/dL based on urate level measurement that will occur at the Week 3, Week 6, Week 9, Week 12 and Week 16 visits. Clinic visits will occur at Screening, Baseline, Week 12, Week 20 and Unscheduled Safety Visits. Telephone visits and remote serum urate testing will occur at Week 3, Week 6, Week 9 and Week 16. There will be a window of ± 3 days for each visit. The Screening Visit must be completed within 21 days of the Baseline Visit. All visit windows are consecutive calendar days and are calculated from the day the participant starts study treatment (Day 0, the day of the Baseline Visit).

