5 SELECTION AND WITHDRAWAL OF STUDY POPULATION

5.1 Number of Study Subjects

Approximately 60 subjects will be consented for the study. Any subject who signs consent will be considered enrolled in the study. Screening study procedures will begin after informed consent.

We expect a 50% screen fail rate based on our goal of elevating serum urate levels only in those subjects whose serum urate level falls below the population median. This subpopulation is at greater risk of faster disease progression and can also accommodate an increase in serum urate to higher, but still normal levels, which are known to be associated with slower disease progression^{21, 31, 35}.

Thirty (30) subjects will receive inosine or placebo for 20 weeks per study protocol and will be followed up to Week 24.

If a subject fails screening, at a minimum, the following information will be captured and entered in the data capture system: inclusion/exclusion criteria, demographics, screening lab results, reason for screen failure.

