5.2.2 Subject Exclusion Criteria

Study subjects meeting any of the following criteria during screening evaluations will be excluded from entry into the study:

1. History of urolithiasis.
2. Urine pH < 5.5 at screening (as acidic urine is a major determinant of uric acid urolithiasis).
3. History of gout.
4. History of stroke or myocardial infarction.
5. History of symptomatic coronary artery disease (e.g. angina pectoris) or symptomatic peripheral arterial disease within 1 year prior to Screening.
6. Symptomatic congestive heart failure with a documented ejection fraction below 45%.
7. Poorly controlled arterial hypertension (SBP>160mmHg or DBP>100mmHg at Screening).
8. Women who are pregnant or lactating.
9. The presence of unstable psychiatric disease, cognitive impairment, or dementia that would impair ability of the subject to provide informed consent, according to Site Investigator judgment, or a history of active substance abuse within the prior year.
10. Anything that, in the opinion of the Site Investigator, would place the subject at increased risk or preclude the subject's full compliance with or completion of the study.
11. Use of the following within 30 days prior to Screening: inosine, allopurinol, probenecid, more than 300mg vitamin C daily (note that a subject may take a standard multivitamin up to one tablet or capsule daily). Use of thiazides is permissible as long as the subject is on a stable dose from 1 week prior to Screening.
12. Known hypersensitivity or intolerability to inosine.
13. Renal insufficiency as defined by eGFR < 60 mL/min/1.73m² at Screening.

Participation in other investigational trials for the treatment of patients with ALS is allowed.

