9.1 Definitions of AEs, Suspected Adverse Drug Reactions & SAEs

9.1.1 Adverse Event and Suspected Adverse Drug Reactions

An adverse event (AE) is any unfavorable and unintended sign (including a clinically significant abnormal laboratory finding, for example), symptom, or disease temporally associated with a study, use of a drug product or device whether or not considered related to the drug product or device.

Adverse drug reactions (ADR) are all noxious and unintended responses to a medicinal product related to any dose. The phrase “responses to a medicinal product” means that a causal relationship between a medicinal product and an adverse event is at least a reasonable possibility, i.e., the relationship cannot be ruled out. Therefore, a subset of AEs can be classified as suspected ADRs, if there is a causal relationship to the medicinal product.

Examples of adverse events include: new conditions, worsening of pre-existing conditions, clinically significant abnormal physical examination signs (i.e. skin rash, peripheral edema, etc), or clinically significant abnormal test results (i.e. lab values or vital signs), with the exception of outcome measure results, which are not being recorded as adverse events in this trial (they are being collected, but analyzed separately). Stable chronic conditions (i.e., diabetes, arthritis) that are present prior to the start of the study and do not worsen during the trial are NOT considered adverse events. Chronic conditions that occur more frequently (for intermittent conditions) or with greater severity, would be considered as worsened and therefore would be recorded as adverse events.

Adverse events are generally detected in two ways:

Clinical → symptoms reported by the subject or signs detected on examination.

Ancillary Tests → abnormalities of vital signs, laboratory tests, and other diagnostic procedures (other than the outcome measures, the results of which are not being captured as AEs).

For the purposes of this study, symptoms of progression/worsening of ALS, including ‘normal’ progression, will be recorded as adverse events.

The following measures of disease progression will not be recorded as adverse events even if they worsen (they are being recorded and analyzed separately): vital capacity results and ALSFRS-R results.

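### Treatment-emergent is defined by time alone, so an unchanged pre-dose lab or vital-sign abnormality can be counted as an event and inflate the reported rates

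*Combined protocol and SAP*

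**What the plan says.** Section 10.2.2.1 compares the arms on the proportion of subjects with "one or more treatment-emergent (TE, defined as occurring any time after first dose of study drug) AEs". That bracket is the only definition of treatment-emergent in the document, and it is a rule about time.

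The next sentence of 10.2.2.1 sets up separate comparisons of the proportion with "one or more TE clinically significant abnormal labs for each safety assay performed or clinically significant abnormal vital signs for each vital sign monitored". The label TE is attached to labs and is not repeated for vital signs. Neither part asks whether the abnormality was there before the first dose or has become worse. The test is Fisher's exact, but this sentence states no sidedness or alpha; both are stated for the AE comparisons.

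Three other places bear on the point:

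- **Section 9.1.1, AEs.** Stable chronic conditions "that are present prior to the start of the study and do not worsen during the trial are NOT considered adverse events". The same section gives clinically significant abnormal test results as examples of AEs, and leaves it to the Site Investigator to identify which lab abnormalities are clinically significant.
- **Section 5.2.2, entry.** Blood pressure excludes a subject only above 160 systolic or 100 diastolic at Screening. Renal function has an eGFR limit of 60. Haematology and liver tests have no limit.
- **Sections 7.1, 7.2 and the Schedule of Activities.** Safety labs are drawn at the Baseline Visit. Vital signs are taken at Screening and are not listed at Baseline.

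**The concern.** Safety is one of the two primary outcomes (Section 3.2), so the event rule for its tables matters.

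Take two subjects whose Week 12 systolic pressure is 155 and is judged clinically significant. One had 155 at Screening and the other had 125. The rule counts both as events, although only the second had anything emerge on treatment. The same holds for a liver test that was raised to the same level in the Baseline sample. Blood pressure is a relevant measure here, because Section 2.3.1 notes that high urate has been associated with high blood pressure.

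Three things are at stake. The rates reported as treatment-emergent would include abnormalities that treatment could not have caused. Relative comparisons between arms would be pulled towards no difference. And because the text does not settle the rule, two analysts could build different tables from the same data.

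**Working it through.** **Inputs**

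- Allocation and size: subjects "will be randomized 2:1 to receive inosine or placebo" (Section 4.1), and "Thirty (30) subjects will receive inosine or placebo for 20 weeks per study protocol" (Section 5.1), hence 20 inosine and 10 placebo. The Study Workflow shows 15 and 15; the plan's own AE power figures match 20:10, so 20:10 is used.
- Test: one-tailed Fisher's exact at 0.05, as stated for AEs in 10.2.2.1. For labs and vital signs this is an assumption.
- b = share of subjects with a stable, clinically significant pre-dose abnormality on the measure. The documents do not give it; 20% is assumed, with 10% and 30% alongside.
- p1, p0 = new-onset rates on inosine and placebo among subjects without a pre-dose abnormality. The pair 59% and 10% is borrowed from Section 10.2.2.5, where it refers to AEs.

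**Step 1: reproduce the plan's figure.** Exact enumeration at 20:10 gives power of 79.7% for 95% vs 50%, 80.1% for 71% vs 20%, and 79.7% for 59% vs 10%. The plan states 80% for each.

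**Step 2: what the literal rule reports.** Counted rate = b + (1 − b)p. With b = 0.20:

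- Inosine: 0.20 + 0.80 × 0.59 = 0.672
- Placebo: 0.20 + 0.80 × 0.10 = 0.280
- Risk ratio: 0.672 / 0.280 = 2.4
- Risk difference: 0.672 − 0.280 = 0.392

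**Step 3: what a new-events rule reports, all subjects in the denominator.** Rate = (1 − b)p:

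- Inosine: 0.80 × 0.59 = 0.472
- Placebo: 0.80 × 0.10 = 0.080
- Risk ratio: 0.472 / 0.080 = 5.9
- Risk difference: 0.472 − 0.080 = 0.392

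The risk difference is (1 − b)(p1 − p0) under both rules, because b cancels in the subtraction. If there were no new events on placebo, the literal rule would still report a placebo rate of 20%.

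**Step 4: power, one-tailed, 20:10.**

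| New onset, inosine vs placebo | b | Literal rule | New events, all subjects |
|---|---|---|---|
| 59% vs 10% | 10% | 66.9% | 70.8% |
| 59% vs 10% | 20% | 55.1% | 60.6% |
| 59% vs 10% | 30% | 44.1% | 49.3% |
| 40% vs 0% | 10% | 51.3% | 62.0% |
| 40% vs 0% | 20% | 39.1% | 46.9% |
| 40% vs 0% | 30% | 31.0% | 31.7% |
| 30% vs 0% | 10% | 29.8% | 28.1% |
| 30% vs 0% | 20% | 22.9% | 18.4% |

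Restricting the denominator to subjects normal before dosing gives 65.1% for 59% vs 10% at b = 20%.

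**Step 5: two-sided.** The same enumeration with a two-sided Fisher test at b = 20% gives 42.0% (literal) against 54.0% (new events, all subjects) for 59% vs 10%, and 30.5% against 29.2% for 40% vs 0%. The sign again depends on the event rates.

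**The case against.** **Section 9.1.1 already excludes stable conditions.** That section names clinically significant abnormal labs and vital signs as examples of AEs and, in the same paragraph, leaves out stable chronic conditions. A reader could carry the exclusion over to the lab and vital-sign tables. For AEs this stands, and they are largely protected. But the exclusion defines what is an AE, while 10.2.2.1 analyses labs and vital signs separately, per assay and per sign, without invoking it.

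**Only clinically significant abnormalities count.** This also stands as a limit. For labs the Site Investigator decides, and a pre-dose value accepted at entry may well not be judged significant later. So b may be well below the share of subjects with out-of-range values. Yet significance is not emergence: a stable abnormality can still meet the one example given, a need for intervention.

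**A stronger reading is tempting: that the rule costs the safety comparison a large share of its power.** At b = 20%, power for 59% vs 10% is 55.1% under the literal rule against 79.7% with nobody abnormal at entry, a fall of 24.6 points. The documents do not support charging that to the definition. A subject with a stable pre-dose abnormality cannot have a new one, so better wording cannot restore 79.7%; it gives 60.6%. The definition accounts for 60.6 − 55.1 = 5.5 points, and at 30% vs 0% the literal rule has the higher power. Nor is any stated power figure undermined, since Section 10.2.2.5 makes AE claims and none about labs or vital signs.

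**Conclusion.** The point holds as one about what the tables report. The definition in 10.2.2.1 rests on time alone, is applied to labs, is missing from the vital-sign clause, and has no pre-dose comparison. Taken literally, unchanged pre-dose abnormalities that are still judged clinically significant count in both arms. Rates are overstated and the risk ratio moves towards 1, while the risk difference is unchanged from counting new events over all subjects.

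The size depends on b, which is assumed. At 20%, rates of 47.2% and 8.0% for new events over all subjects (new onset 59% and 10%) are reported as 67.2% and 28.0%, and the risk ratio falls from 5.9 to 2.4. The calculation also assumes that affected subjects stay stable and that b is equal in the two arms.

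No general claim about power is warranted. The difference between the rules is modest in most of the cases worked, 12 points at most, and its sign varies with the event rates and the sidedness. This should be corrected before analysis, but it does not threaten the conduct of the trial.

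**What to change.** In Section 10.2.2.1:

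- State that, for labs and vital signs, treatment-emergent means clinically significant abnormal after the first dose and either not abnormal at the last pre-dose measurement or worse than it by a pre-stated step.
- Name the reference: Baseline for safety labs, Screening for vital signs.
- Apply the label to the vital-sign clause as well.
- State whether subjects abnormal before dosing stay in the denominator, and give the sidedness and alpha of these tests.
- Report persistent pre-existing abnormalities separately, in a shift table by arm.

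The cost is SAP wording only, since the pre-dose values are already collected. A step for worsening has to be set for each measure, and power may be slightly lower at some event rates.

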⁴ Screening labs include uric acid, urinalysis and Serum pregnancy test (WOCBP) and will be performed at local institution.

Inosine in ALS

V3.0

7/01/2019

⁵ Uric acid level will be measured just before the first dose (Baseline visit) or just before scheduled morning dose (trough) (Weeks 3, 6, 9, 12, 16, 20) (Quest Diagnostics)

⁶ Urinalysis with sediment (Quest Diagnostics)

⁷ Safety labs include Hematology (CBC with differential), Basic Metabolic Panel, Liver Function Tests and will be performed at local institution.

⁸ Pulmonary Function Testing includes Slow Vital Capacity (SVC)

⁹ Adverse events that occur AFTER signing consent form will be recorded.

¹⁰ App installation and un-installation procedures include a brief survey about phone use

STUDY WORKFLOW

[figure not shown]
Screening Period

On Active Treatment

Washout Period

[figure not shown]
[figure not shown]
~ 60 Screened

15 Subjects on inosine (administered as 500 mg caps; 1 to 6 caps a day; dose titrated to target urate levels of 7 - 8 mg/dL).

15 Subjects on placebo (administered as 500 mg caps; 1 to 6 caps a day; pseudo-titration will be performed to maintain blinding).

21 Days

Subjects who discontinue from the study early will be asked to return to the study site for Final Safety assessments, and will be asked to have a final Follow-Up Telephone Call 28 days (+5 days) after taking their last dose of study drug.

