10.2.2.5 Power Calculations

Assuming that 50%, 20%, and 10% of participants in the placebo group are expected to experience an AE or a given type of AE, we will have 80% power to declare a significant treatment-dependent increase in the proportion experiencing an AE if at least 95%, 71%, and 59% of participants in the inosine group are expected to experience an AE, respectively. We will have 80% power to observing at least one instance of any inosine-associated AE with a true probability of occurrence of at least 8%. For tolerability, we will have 80% power to declare inosine tolerable if the true proportion tolerant is at least 71%. Variance component estimates for calculating power for effects of treatment on ALSFRS-R are from a single arm pilot study of 25 participants on inosine for 20 weeks. Based on the follow-up schedule for this trial and assuming a random-slopes model, the estimated effective SD for ALSFRS-R slope per month is 1.4. Given this estimate, we will have 80% power to detect a difference in ALSFRS-R slopes between the inosine and placebo groups of 1.05 units per month. We will have 12% power for a difference in slopes of 0.3 units per month.

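### The one-tailed Fisher tests on AE proportions are valid but use at most 2.6% of their 5% level at 20:10; Boschloo's test would lift power from about 80% to 87–89% at no cost in subjects

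*Combined protocol and SAP*

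**What the plan says.** Safety, measured by adverse events, is a primary outcome (section 3.2). Section 10.2.2.1 lists the proportions of subjects with any, severe, serious and special-interest treatment-emergent AEs, and with AEs by MedDRA system organ class, higher level term and preferred term. The inosine proportions are set against placebo by "one-tailed Fisher's exact tests" at a level of 0.05.

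Section 10.2.2.5 sets the planning cases: "Assuming that 50%, 20%, and 10% of participants in the placebo group are expected to experience an AE" or a given type of AE, the trial has 80% power "if at least 95%, 71%, and 59% of participants in the inosine group are expected to experience an AE", in the same order.

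On sample size, section 4.1 says "Approximately 30 of these subjects are expected to be found eligible for study enrollment" and that they "will be randomized 2:1 to receive inosine or placebo", which is 20:10. The Study Workflow in the Protocol Summary shows equal groups ("15 Subjects on placebo"). The plan does not mention the true size of Fisher's test at these numbers, or any unconditional or mid-p alternative. The only other AE analysis named is a negative binomial sensitivity analysis of event rates.

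**The concern.** The sponsor chose to accept a one-tailed 5% error to detect excess harm. Fisher's test conditions on the total number of events, and with 30 subjects the possible p-values are so coarse that much of the 5% cannot be used. In a small safety trial whose detectable excesses are already 45, 51 and 49 percentage points, unused error is power given up on a primary outcome. If another exact test rejects in every case where Fisher's does, rejects in some more, and still respects the 5% limit, the plan gains power without adding a subject.

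**Working it through.** **Inputs.** n₁ = 20 inosine and n₂ = 10 placebo (section 4.1); one-tailed level 0.05 (10.2.2.1); rates 50/95%, 20/71% and 10/59% (10.2.2.5).

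**Formulas.** With x events on inosine and y on placebo, there are 21 × 11 = 231 tables.

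- Fisher p(x, y) = P(X ≥ x), with X hypergeometric given the total x + y. The Fisher region is p ≤ 0.05.
- Power = sum over rejected tables of Bin(x; 20, p₁) × Bin(y; 10, p₂).
- Size = maximum of the same sum with p₁ = p₂ = p, over p (grid of 1,999 points from 0.0005 to 0.9995).
- Boschloo: reject when the Fisher p-value is at or below a cut-off c, where c is the largest value that keeps size ≤ 0.05. Here c = 0.0952.

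**Step 1: reproduce the plan's power.**

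| Method | 50 vs 95% | 20 vs 71% | 10 vs 59% |
|---|---|---|---|
| Fisher, one-tailed 0.05, 20:10 | 79.7% | 80.1% | 79.7% |
| Fisher, one-tailed 0.05, 15:15 | 84.3% | 82.4% | 83.1% |
| Fisher, two-sided, 20:10 | 79.7% | 68.4% | 71.9% |
| Fisher, one-tailed 0.025, 20:10 | 62.8% | 66.4% | 67.0% |
| Normal approximation, one-sided, 20:10 | 88.1% | 88.2% | 88.6% |

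Of these, only one-tailed Fisher at 20:10 gives 80% in all three cases, so the stated power is right for the planned test and rests on 2:1 allocation.

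**Step 2: true size of Fisher.** The maximum is 2.60%, at a common rate near 0.53. It is 2.57% at a 50% rate, 1.00% at 20% and 0.08% at 10%.

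**Step 3: the two rejection regions.** Smallest inosine count that rejects, for each placebo count:

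| Placebo events (of 10) | 0 | 1 | 2 | 3 | 4 | 5 | 6 | 7 |
|---|---|---|---|---|---|---|---|---|
| Fisher (of 20) | 7 | 10 | 12 | 14 | 16 | 18 | 19 | 20 |
| Boschloo (of 20) | 6 | 9 | 11 | 13 | 15 | 17 | 18 | 19 |

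Fisher rejects 14 + 11 + 9 + 7 + 5 + 3 + 2 + 1 = 52 tables. Boschloo rejects the same 52 plus one more in each column, 60 in all. As an example, 6/20 versus 0/10 has Fisher p = C(20,6)/C(30,6) = 38,760/593,775 = 0.065, which is not significant; its Boschloo p is 0.032.

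**Step 4: gain.**

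| | Fisher | Boschloo | Barnard, pooled Z | Barnard, unpooled Z |
|---|---|---|---|---|
| Maximum size | 2.60% | 4.84% | 3.96% | 4.27% |
| Power, 50 vs 95% | 79.7% | 89.5% | 86.6% | 67.8% |
| Power, 20 vs 71% | 80.1% | 87.0% | 80.5% | 80.3% |
| Power, 10 vs 59% | 79.7% | 87.3% | 83.1% | 83.1% |

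Boschloo gains 9.8, 7.0 and 7.5 points. At 80% power the detectable inosine rates move from 95.1/71.0/59.2% to 91.0/66.3/54.3%. At smaller excesses, Fisher to Boschloo: 50 vs 80%, 36% to 48%; 20 vs 50%, 35% to 46%; 10 vs 40%, 37% to 49%.

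**Step 5: where it does not help.** At 1% vs 6%, power goes from 0.01% to 0.08%. At 1.3% vs 3.8% both tests are at about 0.01% or less.

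**Step 6: other group sizes.** At 15:15 Fisher's size is 2.2% and Boschloo gains 6.7 to 8.4 points at the same rates. With as-treated groups of 18–20 versus 9–10, Fisher's size is 2.0–2.4% in the combinations checked and the gain is about 1 to 14 points.

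**The case against.** The strongest reply is that nothing here is wrong. Fisher's test holds its level and the quoted power is correct, so the choice is between two valid exact tests. That stands, and it limits the point to an improvement. A reader might infer from the 2.6% that the plan miscalculated its error rate or its power; step 1 shows that it did not.

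Other objections also stand in part:

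- **False flags.** Section 10.2.2.1 runs the test over every MedDRA level listed and states no multiplicity adjustment. Boschloo raises the per-test rate from 1.0% to 2.4% at a common 20% rate and from 2.6% to 4.6% at 50%. Each test stays within the sponsor's 5%, but over many terms some conservatism is defensible. This favours restricting the change to the headline categories.
- **The known harm.** Section 2.3.1 reports stones in 6% of subjects on inosine in the Parkinson's disease trial, and 3.8% versus 1.3% in the placebo-controlled multiple sclerosis trial. It is tempting to infer that a better test would let this trial detect such an excess. Step 5 shows that it would not. Even at the 25% stone rate of the smaller multiple sclerosis study, assuming none on placebo, power rises only from 21% to 38%.
- **No decision rule.** Safety oversight in section 10.1 runs through the medical safety monitor and the DSMB, and no stopping or go/no-go rule uses these p-values.
- **Conditional inference.** Under a sharp null with re-randomisation both margins are fixed, which leads to Fisher's test, so one cannot claim that only an unconditional test suits the design. The primary sample is also as-treated. This carries little weight here, because the power figures in 10.2.2.5 average over the random number of events and so judge Fisher's test unconditionally.

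Two extensions are not supported. The gain does not belong to unconditional tests in general: pooled-Z Barnard recovers 0.5 to 6.9 points and unpooled-Z Barnard loses 11.9 at 50 vs 95%. Nor should the change be carried to the tolerability comparison in 10.2.2.2, which states no tail or level and whose verdict rests on a single-arm confidence bound.

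**Conclusion.** The point holds as a cheap improvement. At 20:10 the planned one-tailed Fisher tests never use more than 2.6% of their 5%. Boschloo's test at the same level cannot have less power under any alternative, because its rejection region contains Fisher's. It adds 7 to 10 points at the plan's three cases, for a maximum size of 4.8%.

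This assumes 20 and 10 analysed subjects and independent binomial counts. The 7-to-10 range belongs to those three cases: over other alternatives checked, the gain runs from 0 to about 18 points and is near zero for rare events. The finding does not depend on which of the two stated allocations is used.

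**What to change.** Before unblinding:

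1. In 10.2.2.1, name Boschloo's unconditional exact test, one-tailed at 0.05, for the AE proportion comparisons, at least for any, severe, serious and special-interest treatment-emergent AEs. Report Fisher p-values as supportive.
2. In 10.2.2.5, restate the inosine rates detectable with 80% power as about 91%, 66% and 54% for placebo rates of 50%, 20% and 10%, and give the group sizes used.
3. Leave the tolerability comparison in 10.2.2.2 as it is.

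The cost is a few lines of SAP text and a standard software routine, with no extra subjects, visits or procedures. The price is a less familiar test, slightly more computation, and the higher per-test false-flag rate described above.
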